#### **10.2.1.2. Suspected Unexpected Serious Adverse Reactions**

Suspected unexpected serious adverse reactions (SUSARs) are serious events that are not listed in the Development Core Safety Information in the IB and that the investigator identifies as related to the study treatment or study procedure. United States 21 CFR 312.32 and European Union Clinical Trial Directive 2001/20/EC and the associated detailed guidances or national regulatory requirements in participating countries require the reporting of SUSARs. Lilly has procedures that will be followed for the recording and expedited reporting of SUSARs that are consistent with global regulations and associated detailed guidances.

## **10.2.2. Other Safety Measures**

### **10.2.2.1. Electrocardiograms**

For each patient, 12-lead digital ECGs will be collected according to the Study Schedule ([Attachment 1](#)) as single ECGs. Patients must be supine for approximately 5 to 10 minutes before ECG collection and remain supine but awake during ECG collection.

Electrocardiograms may be obtained at additional times, when deemed clinically necessary. Collection of more ECGs than expected at a particular time point is allowed when needed to ensure high-quality records.

Electrocardiograms will be interpreted by a qualified physician (the investigator or qualified designee) at the site as soon after the time of ECG collection as possible, and ideally while the patient is still present, to determine whether the patient meets entry criteria and for immediate patient management, should any clinically relevant findings be identified.

After enrollment, if a clinically significant increase in the QT/corrected QT interval from baseline or other clinically significant quantitative or qualitative change from baseline is identified, the patient will be assessed by the investigator for symptoms (for example, palpitations, near syncope, syncope) and to determine whether the patient can continue in the study. The investigator or qualified designee is responsible for determining if any change in patient management is needed and must document his/her review of the ECG printed at the time of evaluation.

### **10.2.3. Safety Monitoring**

The Lilly CRP will monitor safety data throughout the course of the study.

Lilly will review SAEs within time frames mandated by company procedures. The Lilly CRP or designee will, as is appropriate, consult with the functionally independent Global Patient Safety therapeutic area physician or clinical scientist, and review:

- trends in safety data
- laboratory analytes
- adverse events
- If a patient experiences elevated ALT  $>5 \times$  ULN and elevated total bilirubin  $>2 \times$  ULN, clinical and laboratory monitoring should be initiated by the investigator. For patients entering the study with ALT  $>3 \times$  ULN, monitoring should be triggered at ALT  $>2 \times$  baseline.
- Details for hepatic monitoring depend upon the severity and persistence of observed laboratory test abnormalities. To ensure patient safety and comply with regulatory guidance, the investigator is to consult with the Lilly CRP regarding collection of specific recommended clinical information and follow-up laboratory tests. See [Attachment 3](#).

Information on SAEs expected in the study population independent of drug exposure and that will be assessed by Lilly in aggregate periodically during the course of the trial may be found in the IB. In the NSCLC population, the occurrence of fatigue/weakness/asthenia, pain/chest pain, dyspnea, cough, nausea, anorexia/decreased appetite, disease progression, metastasis, hemoptysis, and pleural effusion are reasonably anticipated due to the underlying malignancy.

#### **10.2.4. Complaint Handling**

Lilly collects product complaints on study drugs used in clinical trials in order to ensure the safety of study participants, monitor quality, and to facilitate process and product improvements.

Complaints related to concomitant drugs/drug delivery systems are reported directly to the manufacturers of those drugs/devices in accordance with the package insert.

The investigator or his/her designee is responsible for handling the following aspects of the product complaint process in accordance with the instructions provided for this study:

- recording a complete description of the product complaint reported and any associated AEs using the study-specific complaint forms provided for this purpose
- faxing the completed product complaint form within 24 hours to Lilly or its designee

If the investigator is asked to return the product for investigation, he/she will return a copy of the product complaint form with the product.

### **10.3. Sample Collection and Testing**

Samples collected for this study will be coded with the patient number. The samples and any data generated from them can be linked back to the patient only by investigator site personnel.

[Attachment 1](#) lists the schedule for sample collections in this study.

[Attachment 2](#) lists the specific tests that will be performed for this study and whether these will be performed at a central or local laboratory.

[Attachment 7](#) provides a summary of the estimated maximum number and volume of invasive samples, for all sampling, during the study.

#### **10.3.1. Samples for Study Qualification and Health Monitoring**

Standard laboratory tests, including chemistry, hematology, coagulation, and pregnancy testing (if applicable in women of childbearing potential), will be performed and analyzed centrally.

Urinalysis will be assayed by investigator-designated (local) laboratory. [Attachment 2](#) lists the laboratory tests that will be performed for this study. Central laboratory results will be used to determine patient eligibility at baseline. Local laboratory results may be used for on-study dosing decisions; if so, testing must also still be performed by the central laboratory. These central laboratory results will be used for subsequent safety analyses. In the event of minor discrepancies between local and central laboratory results, the investigator may use the local results for treatment decisions, and the central laboratory results will remain part of the safety database.

Blood and urine samples will be collected at the times specified in the Study Schedule ([Attachment 1](#)).

Based on laboratory safety values, unscheduled hepatic monitoring tests (see [Attachment 3](#)) may be performed as part of patient follow-up, in consultation with the Lilly CRP.

Investigators must document their review of each laboratory safety report.

Samples collected for specified laboratory tests will be destroyed within 60 days of receipt of confirmed test results. Tests are run and confirmed promptly whenever scientifically appropriate. When scientific circumstances warrant, however, it is acceptable to retain samples to batch the tests run, or to retain the samples until the end of the study to confirm that the results are valid. Certain samples may be retained for a longer period, if necessary, to comply with applicable laws, regulations, or laboratory certification standards.

### **10.3.2. Samples for Pharmacogenetics and Translational Research**

Collection of samples for translational research is also part of this study.

Required samples for biomarker research to be collected from all patients in this study are the following:

- Whole blood
- Plasma
- Archived tumor tissue (a minimum of 12 slides is required for study eligibility)

As part of an ongoing effort by Lilly to better understand how to predict which patients are more likely to respond to necitumumab and abemaciclib treatment, whole blood, plasma, and tissue samples will be collected to explore biomarkers including but not limited to, those related to the EGFR pathway, Rb pathway, CDK4/6, cell cycle, and/or the pathogenesis of lung cancer. Analyses may include, but are not limited to, potential nucleic acid and protein markers to better understand the disease process, and to develop predictive biomarkers and diagnostics.

#### **10.3.2.1. Samples for Pharmacogenetic Evaluation**

There is growing evidence that genetic variation may impact a patient's response to therapy. Variable response to therapy may be due to genetic determinants that impact drug absorption, distribution, metabolism, and excretion, the mechanism of action of the drug, the disease etiology and/or the molecular subtype of the disease being treated. Therefore, where local regulations and ERBs allow, a whole blood sample will be collected for pharmacogenetic analysis. It is a 1-time collection, as noted in the Study Schedule ([Attachment 1](#)).

Samples will be stored and analysis may be performed on genetic variants thought to play a role in the EGFR-pathway, Rb pathway, CDK4/6, cell cycle, NSCLC pathogenesis, and the mechanism of action of necitumumab or abemaciclib to evaluate their association with observed clinical outcomes (OS, PFS, and ORR).

In the event of an unexpected AE or the observation of unusual response, the pharmacogenetic biomarker samples may be genotyped and analysis may be performed to evaluate a genetic

association with response to necitumumab or abemaciclib. These investigations may be limited to a focused candidate gene study or, if appropriate, genome-wide analysis may be performed to identify regions of the genome associated with the variability observed in drug response. The pharmacogenetic biomarker samples will only be used for investigations related to disease and drug or class of drugs under study in the context of this clinical program. They will not be used for broad exploratory unspecified disease or population genetic analysis.

The samples will be coded with the patient number and stored for up to a maximum 15 years after the last patient visit for the study at a facility selected by the sponsor. The samples and any data generated from them can only be linked back to the patient by investigator site personnel. The duration allows the sponsor to respond to regulatory requests related to the study drugs.

Samples will be destroyed according to a process consistent with local regulation.

### **10.3.2.2. Archived Tumor Tissue Collection**

To meet study eligibility criteria, and therefore mandatory for study participation, patients must have available formalin fixed-paraffin embedded (FFPE) tumor sample. While the tissue can be from either initial diagnosis of Stage IV NSCLC or later (for example, at relapse), the most recent sample is preferred. The sample can be either 12 serially cut unstained sections or a tissue block (preferred). Due diligence should be used to make sure that tumor specimens (not a normal adjacent or a tumor margin sample) are provided. Available FFPE primary and/or metastatic tumor tissue should be in a whole block, partial block, or unstained slides. Archived tumor tissue must be made available for biomarker assessments. If tumor tissue (primary or metastatic site, paraffin-embedded) is available from a recent biopsy performed as a part of routine clinical care prior to screening, this may be used if archived tissue is not available. If the required amount of tumor tissue is not available, the patient may still be eligible if willing to undergo a tumor biopsy and if the procedure is considered safe and feasible at the investigator's discretion. Cytologic samples and fine-needle aspiration specimens are not acceptable. Pathology notes accompanying archival tissue may also be requested.

In tumor tissue samples, the CDK4/6 and EGFR pathway components and markers relevant to NSCLC pathogenesis may be evaluated to assess any potential correlation with response to therapy. Tumor samples may be analyzed to explore potential tumor gene signature(s) associated with response or resistance to abemaciclib and/or necitumumab therapy. These studies may be analyzed at a laboratory designated by the sponsor and may include, but are not limited to, immunohistochemistry of proteins, FISH for copy number amplifications, RNA gene-expression profiling, and/or genetic analyses of the tumor specimen DNA. Such analyses may employ targeted or high-throughput sequencing approaches. For this purpose, the results of this analysis will be correlated with clinical efficacy data.

Samples will be identified by the patient number (coded) and stored for up to a maximum of 15 years after the last patient visit for the study at a facility selected by the sponsor. After testing has been completed, the paraffin-embedded whole blocks will be returned to the sites. Whole blocks can be returned sooner, if requested by the sites. Partial blocks and slides will not be returned.

### **10.3.2.3. Plasma Sample Collection**

At the visits and times specified in [Attachment 7](#), EDTA-anticoagulated plasma will be collected for exploratory biomarker analyses that may include, but are not limited to, exosomes, nucleic acid and protein markers indicative of the pathobiology of the tumor, expected mechanisms of action of the therapy, responses to treatment, and molecular pathways.

The samples will be coded with the patient number and stored for up to a maximum 15 years after the last patient visit for the study at a facility selected by the sponsor. The samples and any data generated from them can only be linked back to the patient by investigator site personnel. The duration allows the sponsor to respond to regulatory requests related to the study drugs.

### **10.3.3. Samples for Immunogenicity Research**

Blood samples for immunogenicity testing will be collected at time points specified in [Attachment 7](#) to determine antibody production against necitumumab. The actual date and time of collection of each sample will be recorded. Immunogenicity will be assessed by a validated assay designed to detect anti-drug antibodies in the presence of the necitumumab. Antibodies may be further characterized and/or evaluated for their ability to neutralize the activity of necitumumab.

As noted in Section [9.3.2.2.3.1](#), a sample for evaluation of antibodies against necitumumab will also be collected in the setting of an infusion-related/hypersensitivity reaction to necitumumab (as close to the onset of the event as possible, at the resolution of the event, and 30 days following the event). When any immunogenicity sample is drawn, a sample for necitumumab concentration measurement (PK) should also be drawn (immunogenicity and PK samples to be collected from 2 separate blood draws, within no more than 15 minutes' time difference), to allow interpretation of immune response (see Section [10.3.4](#)).

Samples may be stored for a maximum of 15 years following last patient visit for the trial at a facility selected by the sponsor to enable further analysis of immune responses to necitumumab. The duration allows the sponsor to respond to regulatory requests related to necitumumab.

### **10.3.4. Samples for Drug Concentration Measurements Pharmacokinetics**

Pharmacokinetic (PK) samples (venous blood) will be collected as specified in the Pharmacokinetic, Immunogenicity, and Blood Based Markers Sampling Schedule ([Attachment 7](#)). Blood samples will be collected to determine the serum concentrations of necitumumab using a validated enzyme-linked immunosorbent assay method at a laboratory approved by the sponsor.

Blood samples will also be collected to determine the plasma concentrations of abemaciclib and metabolites using a validated liquid chromatography–tandem mass spectrometry method.

Bioanalytical samples collected to measure necitumumab and abemaciclib (and metabolites) concentrations will be retained for a maximum of 1 year following last patient visit for the study.

#### **10.4. Appropriateness of Measurements**

The measures used to assess safety and efficacy in this study are consistent with those used in most conventional oncology trials

## 11. Data Quality Assurance

To ensure accurate, complete, and reliable data, Lilly or its representatives will do the following:

- provide instructional material to the study sites, as appropriate
- sponsor start-up training to instruct the investigators and study coordinators. This session will give instruction on the protocol, the completion of the CRFs, and study procedures.
- make periodic visits to the study site
- be available for consultation and stay in contact with the study site personnel by mail, telephone, and/or fax
- review and evaluate CRF data and use standard computer edits to detect errors in data collection
- conduct a quality review of the database

In addition, Lilly or its representatives will periodically check a sample of the patient data recorded against source documents at the study site. The study may be audited by Lilly or its representatives, and/or regulatory agencies at any time. Investigators will be given notice before an audit occurs.

To ensure the safety of participants in the study, and to ensure accurate, complete, and reliable data, the investigator will keep records of laboratory tests, clinical notes, and patient medical records in the patient files as original source documents for the study. If requested, the investigator will provide Lilly, applicable regulatory agencies, and applicable ERBs with direct access to original source documents.

### 11.1. Data Capture System

An electronic data capture system will be used in this trial. The site maintains a separate source for the data entered by the site into the sponsor-provided electronic data capture system.

Case report form data will be encoded and stored in a clinical trial database. Data managed by a central vendor, such as laboratory test data, will be stored electronically in the central vendor's database system. Data will subsequently be transferred from the central vendor to the Lilly generic labs system.

Any data for which the paper documentation provided by the patient will serve as the source document will be identified and documented by each site in that site's study file. Paper documentation provided by the patient may include, for example, a paper diary to collect daily dosing schedule.

Data from complaint forms submitted to Lilly will be encoded and stored in the global product complaint management system.

## 12. Sample Size and Statistical Methods

### 12.1. Determination of Sample Size

A total of approximately 68 patients evaluable for either the Part A or Part B portions of the study will be enrolled. Part A requires up to 18 treated patients (3-6 per dosage cohort). Patients with squamous and nonsquamous NSCLC who received the recommended abemaciclib dose for Part B in Part A will also be part of the Part B portion of the trial. These patients will also be included in the interim analyses as described in Section 12.2.10.

An evaluable patient for Part B will include any patient enrolled in Part A and treated at the recommended doses of necitumumab and abemaciclib. In addition, patients will be entered strictly to Part B (with a total of 50 evaluable patients in Part B). To be evaluable for Part B of the study, these additional patients entered must meet the following criteria:

- (1) The patient has received at least 1 dose each of necitumumab and abemaciclib.
- (2) The patient has a complete radiographic assessment at baseline.

The final analysis of the study will take place approximately 5 months after the last patient evaluable for Part B portion of the study has been enrolled. The primary Part B outcome variable in this study will be the 3-month PFS rate. The Part B statistical null hypothesis states that the true 3-month PFS rate is 50%, whereas the research hypothesis states that the true 3-month PFS rate is 65%. Assuming the Part B portion of the study continues to a full enrollment of 50 evaluable patients, the null hypothesis will be rejected at the final analysis only if at least 60% of evaluable patients experience PFS  $\geq 3$  months.

If the research hypothesis is true, there is an 81% chance of reaching full Part B enrollment and rejecting the null hypothesis. If the null hypothesis is true, then there is a 10% chance of reaching full Part B enrollment and rejecting the null hypothesis. Therefore, the Part B portion of this study has a one-sided alpha level of 0.10, with statistical power of 81%.

### 12.2. Statistical and Analytical Plans

#### 12.2.1. General Considerations

The primary analysis will be as described in Section 12.1.

All summary analyses, including efficacy and safety analyses, will be performed for all patients enrolled in the study who receive any amount of study drug (necitumumab and abemaciclib).

Minor changes or clarifications to any statistical analyses described in this protocol may be presented in the final statistical analysis plan (SAP) for this study.

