5.2. General Considerations

The following populations will be defined for this study:

- **All enrolled population:** anyone who signed the informed consent will be included in this population.
- **Safety population:** all patients who have received any amount of study drug [necitumumab, and/or abemaciclib]
- **Evaluable population:** all patients who have received at least 1 dose each of necitumumab and abemaciclib and have had a complete radiographic assessment at baseline

Unless otherwise specified, for continuous variables, summary statistics will include number of patients, mean, median, standard deviation, minimum, and maximum. Categorical variables will be summarized using frequency and percentages.

- **Age (years):** $(\text{Informed Consent Date} - \text{Date of Birth} + 1)/365.25$, if only year of birth is collected, see Section 5.3 for date imputation.
- **Missing Data:** All analyses and descriptive summaries will be based on the observed data. Unless otherwise specified, missing data will not be imputed or “carried forward.”
- **Baseline Measurement:** Unless otherwise specified, the last nonmissing measurement prior to the first dose of study drug will serve as the baseline measurement.
- **Study Day:** Study day is calculated as assessment date – first dose date + 1 day if the assessment is done on or after the first dose day. If the assessment is done prior to the first dose day, study day will be calculated as assessment date – first dose date. Date of first dose is defined as study day 1.
- **Duration:** Duration is calculated as:
 - Duration (days): $(\text{End Date} - \text{Start Date} + 1)$
 - Duration (weeks): $(\text{End Date} - \text{Start Date} + 1)/7$
 - Duration (months): $(\text{End Date} - \text{Start Date} + 1)/30.4375$ (Days in months = $(1/12) \times \text{average number of days in a year.}$)
 - Duration (years): $(\text{End Date} - \text{Start Date} + 1)/365.25$ (Average days in a year = 365.25, reflecting the Julian Year of 3 years with 365 days each and one leap year of 366 days.)
- **Time-to-event:** The event or censoring time (days) is calculated as:
Date of event/censoring – Date of first dose of study drug + 1

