5.6. Efficacy Analyses

Efficacy analyses will be performed for the evaluable population. For all time-to-event variables (OS and PFS), the Kaplan-Meier product limit method will be used to estimate the survival curve as well as survival rates at various time points (3-month, 6-month, and 1-year). A 2-sided, 95% confidence interval (CI) for median PFS, median OS, and survival rate at time point will be computed by the Brookmeyer and Crowley method.

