5.6.1. Primary Efficacy Endpoint

The primary endpoint for Part B is the PFS rate at 3 months. Progression-free survival rate at 3 months is defined as the rate of PFS at 3 months from the date of first dose of study drug and is determined using the distribution of overall PFS times. The PFS rate at 3 months is estimated using the Kaplan-Meier method.

Progression-free survival is defined as the time from the date of first dose of study drug until first observation of objective (radiographically documented) PD as defined by Response Evaluation Criteria In Solid Tumors Version 1.1 (RECIST 1.1) or death from any cause, whichever comes first. The censoring is taken in the following order:

- If a patient does not have an adequate baseline radiological tumor assessment, then the PFS time will be censored at the date of first study drug, regardless of whether or not objectively determined disease progression or death has been observed for the patient; otherwise,
- If a patient is not known to have died or have objective progression as of the data inclusion cutoff date for the analysis, the PFS time will be censored at the last adequate objective progression-free disease assessment date.

Adequate radiological tumor assessment refers to an assessment with 1 of the following responses: complete response (CR), partial response (PR), stable disease (SD), or PD. If a tumor assessment was done on multiple days, the earliest date for that visit will be used if overall response is PD, and the last date will be used otherwise (censor).

Progression-free survival sensitivity analysis will be performed. The censoring rules for PFS sensitivity analysis are listed in [Table JFCU.5.1](#).

Table JFCU.5.1. Rules for Determining Date of Progression or Censor for PFS Sensitivity Analysis

Situation	Event / Censor	Date of Event or Censor
Tumor progression or death	Event	Earliest date of PD or death
No tumor progression and no death	Censored	Date of last adequate radiological assessment or date of first dose (whichever is later)
unless		
No baseline radiological tumor assessment available	Censored	Date of first dose
No adequate postbaseline radiological tumor assessment available and death reported after 2 scan intervals following first dose	Censored	Date of first dose

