5.6.2.3. Overall Survival

Overall survival duration is measured from the date of first dose of study drug to the date of death from any cause. For each patient who is not known to have died as of the data-inclusion cut-off date for a particular analysis, OS will be censored for that analysis at the date of last contact prior to the data inclusion cutoff date (contacts considered in the determination of last contact date include adverse event date, lesion assessment date, visit date, and last known alive date).

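### The SAP restricts overall survival to evaluable patients, while protocol 12.2.1 places efficacy summaries on all treated patients; OS needs neither a baseline scan nor a second drug.

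*Protocol*

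**What the plan says.** Protocol 12.2.1 (General Considerations) opens with the primary analysis: "The primary analysis will be as described in Section 12.1". Section 12.1 defines that test on 50 evaluable Part B patients. The next sentence of 12.2.1 sets the population for the rest, saying that summary analyses, "including efficacy and safety analyses, will be performed for all patients enrolled in the study who receive any amount of study drug". A parenthesis follows that names the two drugs joined by *and*.

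Protocol Table JFCU.12.1 gives ORR, and through it DCR, a narrower denominator with baseline and postbaseline scan conditions. Its row for median OS and PFS adds no condition.

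SAP 5.6 says: "Efficacy analyses will be performed for the evaluable population". The same paragraph names OS and PFS as the time-to-event variables. SAP 5.2 defines the evaluable population as "all patients who have received at least 1 dose each of necitumumab and abemaciclib and have had a complete radiographic assessment at baseline", and separately defines a safety population of patients given any amount of either drug or both. SAP 5.6.2.3 names no other population for OS and defines it without imaging: "Overall survival duration is measured from the date of first dose of study drug to the date of death from any cause".

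**The concern.** The two documents give different patient sets for OS. The SAP's set is the narrower one, and its two extra conditions have no bearing on whether a death date can be observed. A baseline scan is needed to judge progression or response, but not to record survival.

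Section 12.1 counts towards a target of 50 evaluable patients, so a treated but non-evaluable patient is in effect replaced. If such patients fare worse than the rest, leaving them out raises the OS estimate, and a single-arm study has no control group to offset that.

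There is also a question of authority. Protocol 12.2.1 lets the SAP make minor changes or clarifications. A change in who is counted for survival is hard to call minor, and the SAP's revision history, which lists only major changes since Version 1, does not mention it. Left open, the point allows a choice between two documented OS populations after the results are known.

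**Working it through.** **1. The plan's own design figure.** The rule needs at least 60% of 50 evaluable patients progression-free at 3 months, so 0.60 × 50 = 30 patients. By exact binomial:

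- P(X ≥ 30 | n = 50, p = 0.50) = 0.1013, against the stated one-sided alpha of 0.10.
- P(X ≥ 30 | n = 50, p = 0.65) = 0.8139, against the stated power of 81%.

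Both agree at the printed precision. OS has no test, sample size or power statement, so nothing below changes these figures.

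**2. Populations side by side.**

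| Analysis | Protocol | SAP | Conflict with 12.2.1? |
|---|---|---|---|
| 3-month PFS decision rule | 12.1: evaluable | 5.1, 5.6: evaluable | No |
| ORR, DCR | Table JFCU.12.1: treated, complete baseline scan, at least one complete postbaseline scan | 5.6.2.1, 5.6.2.2: evaluable | No; own denominator |
| OS | 12.2.1: all treated | 5.6: evaluable | Yes |
| PFS as a secondary summary | 12.2.1: all treated | 5.6: evaluable | Yes, with little effect (step 4) |

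**3. Who drops out of OS.**

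- Treated patients without a complete baseline scan: dropped by the SAP and kept by protocol 12.2.1, however the drug wording is read.
- Patients who received only one drug: dropped by the SAP. Whether the protocol keeps them is unclear. Section 12.2.1 joins the drugs with *and*; the synopsis safety paragraph and Table JFCU.12.1 use *or*; the SAP safety population uses *and/or*.

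**4. Secondary PFS.** Protocol 10.1.3 and SAP 5.6.1 both censor a patient without a baseline assessment at the time origin (enrolment and first dose respectively). Adding such patients back leaves the Kaplan-Meier curve essentially unchanged. Only one-drug patients could move it.

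**5. Size for OS.** The documents give neither an OS rate nor a count of non-evaluable patients, so both are assumed. Let S be landmark OS in the 50 evaluable patients, k the number of treated patients excluded, and q their OS, with no censoring before the landmark.

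OS in all treated = (50S + kq) / (50 + k); overstatement = k(S − q) / (50 + k).

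With S = 0.70 and q = 0 (every excluded patient dies early):

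- k = 1: 35/51 = 68.6%, overstatement 1.4 points
- k = 2: 35/52 = 67.3%, overstatement 2.7 points
- k = 3: 35/53 = 66.0%, overstatement 4.0 points

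With q = S, or with k = 0, the overstatement is zero. With S = 0.60, it runs from 0 (q = S) to 2.3 points (q = 0: 30/52 = 57.7%) for k = 2, and from 0 to 5.5 points (30/55 = 54.5%) for k = 5. For scale, the binomial standard error at S = 0.70 is √(0.70 × 0.30 / 50) = 0.065, or 6.5 points.

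**The case against.** The best defence is that the mismatch is small and touches a secondary estimate. Measurable disease is an entry criterion, baseline tumour measurement is required within 21 days before the first dose, and eligibility waivers are not permitted, so a treated patient without a baseline scan should be rare. Protocol 9.1 places the abemaciclib dose within 10 minutes of the start of the necitumumab infusion, which leaves little room for a one-drug patient. Section 8.2 calls the outcome hypothesis-generating only, and even the worst case for three patients lies within one standard error. All of this stands. It limits the size but does not remove the contradiction.

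A reader might also infer more than the documents support:

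- *That every efficacy analysis conflicts.* The primary rule agrees in both documents, and ORR and DCR have their own denominator. For those two the SAP drops the protocol's postbaseline-scan condition and so keeps early dropouts, which is no tilt towards a favourable result.
- *That one-drug patients are certainly in the protocol's set.* Read literally, the *and* in 12.2.1 excludes them there too.
- *That early deaths are removed.* A patient who dies after one dose of each drug, with a complete baseline scan, stays evaluable and counts as an OS event. A missing baseline scan predates treatment and is not itself an outcome.
- *That the SAP's censoring rule beginning "If a patient does not have an adequate baseline radiological tumor assessment" can never apply.* Protocol 12.1 and SAP 5.1 count Part A patients treated at the recommended doses as evaluable for Part B without restating the scan condition, so the rule could still act on one of them. It largely overlaps with the exclusion in SAP 5.2, but it is harmless.

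**Conclusion.** The conflict holds for OS. Protocol 12.2.1 places it on all treated patients; SAP 5.6 and 5.2 place it on patients with both drugs and a complete baseline scan, and OS requires neither. The missing-scan part stands on any reading. The one-drug part stands only if any amount of study drug means either drug.

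The effect is probably small and may be nil. The 1.4 to 4 points for one to three patients are an upper bound under assumed inputs (70% OS, 50 evaluable patients, early death in all those excluded), not an expected bias. An upward direction is plausible but not shown: it requires the excluded patients to survive less well than the rest. The primary 3-month PFS conclusion, its alpha and its power do not depend on this point. It is still worth settling before results are known, because the correction is specific and cheap.

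**What to change.** - In SAP 5.6 and 5.6.2.3, state that OS is analysed in the safety population (any amount of either drug; for Part B, patients assigned the recommended dose), with evaluable-population OS as a sensitivity analysis.
- In protocol 12.2.1, change the *and* between the two drug names so that it matches the synopsis, Table JFCU.12.1 and the SAP safety population.
- Keep the evaluable set for the 3-month PFS decision rule, and say so in both documents.
- Repeating PFS in all treated patients is optional, since it adds almost nothing for patients without a baseline scan.

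The cost is a few sentences, one extra OS table, and an OS estimate that may be slightly less favourable. No sample size or decision threshold changes.
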